### **4.3. Prior and Concomitant Medications**

Medications collected at screening and during the study will be coded using the current version of the World Health Organization (WHO) Drug dictionary.

#### **4.3.1. Prior Non-Antipruritic Medications**

Prior medications are defined as any medications taken prior to the first dose of study drug. Prior antipruritic therapies are described in [Section 5.4](#) and not repeated here.

Prior medications will be summarized by Anatomical Therapeutic Chemical (ATC) drug class Level 2 and preferred name using the number and percentage of participants for each indication. A participant reporting the same medication more than once will be counted only once when calculating the number and percentage of participants who received that medication. The summary will be ordered alphabetically by ATC medical class and then by preferred term in order of descending overall frequency within each ATC medical class. For drugs with the same frequency, sorting will be done alphabetically.

For the purposes of analysis, any medication with a start date prior to the first dose of study drug will be included in the prior medication summary regardless of when the stop date is. If a partial start date is entered the medication will be considered prior unless the month and year (if day is missing) or year (if day and month are missing) of the start date are after the first dosing date. Medications with a completely missing start date will be included in the prior medication summary, unless otherwise specified.

Summaries will be based on the Safety Analysis Set. No formal statistical testing is planned.

#### **4.3.2. Concomitant Medications**

Concomitant medications are defined as medications taken after the first dose of study drug. Use of concomitant medications will be summarized by ATC drug class Level 2 and preferred name using the number and percentage of participants for each indication. A participant reporting the same medication more than once will be counted only once when calculating the number and percentage of participants who received that medication. The summary will be ordered alphabetically by ATC medical class and then by preferred term in descending overall frequency within each ATC medical class. For drugs with the same frequency, sorting will be done alphabetically.

For the purposes of analysis, any medications with a start date prior to or on the first dosing date of study drug and continued to be taken after the first dosing date, or started after the first dosing date but prior to or on the last dosing date of study drug will be considered concomitant medications. Medications started and stopped on the same day as the first dosing date or the last dosing date of study drug will also be considered concomitant. Medications with a stop date prior to the date of first dosing date of study drug or a start date after the last dosing date of study drug will be excluded from the concomitant medication summary. If a partial stop date is entered, any medication with the month and year (if day is missing) or year (if day and month are missing) prior to the date of first study drug administration will be excluded from the concomitant medication summary. If a partial start date is entered, any medication with the month and year (if day is missing) or year (if day and month are missing) after the study drug stop date will be excluded from the concomitant medication summary. Medications with completely missing start and stop dates will be included in the concomitant medication summary, unless otherwise specified. Summaries will be based on the Safety Analysis Set. No formal statistical testing is planned.

All prior and concomitant medications (other than per-protocol study drugs) will be provided in a by-participant listing sorted by treatment group, participant ID and administration date in chronological order.

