## 7. DISCONTINUATION OF STUDY DRUG AND PARTICIPANT WITHDRAWAL CRITERIA

### 7.1. Discontinuation of Study Drug

Participants may elect to discontinue study drug at any time for any reason.

Whenever possible, participants who discontinue study drug should continue in the study on a weekly visit schedule until completion of F2, 28 ( $\pm 3$ ) days after delivery as outlined in the SoA ([Table 1](#)).

A participant will be discontinued from study drug for any of the following reasons:

- Withdrawal of consent by the participant
- Emergency unblinding of treatment assignment by the investigative site
- Criteria for stopping drug due to suspected DILI are met (refer to [Appendix 3](#))
- Any AE or progression of ICP refractory to rescue medication use that leads the investigator to decide that the participant should be withdrawn from study drug, including but not limited to the following:  
Any AE of Common Terminology Criteria for Adverse Events (CTCAE) Grade 4, related to study drug
- Evidence of hepatic decompensation, including variceal bleeding, hepatic encephalopathy and/or ascites

- In the opinion of the investigator or study medical monitor, it is medically unacceptable or otherwise not in the participant's best interest to continue with study drug
- Gross noncompliance, including failure to adhere to the study requirements as stated in the study protocol.

Refer to the SoA (Table 1) for data to be collected at the time of end of treatment and follow-up and for any further evaluations that need to be completed.

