#### Primary Estimand for Primary Efficacy Endpoint

The primary estimand efficacy endpoint is to evaluate the superior efficacy of volixibat versus placebo for the reduction of elevated sBA concentrations in participants with ICP. The primary comparison of interest is the mean change in sBA concentration comparing baseline with Week 3. The primary comparison will be made regardless of adherence to randomized treatment, treatment modification, or treatment termination and irrespective of any changes in or initiations of allowed concomitant therapies, while assuming that prohibited medications are not available.

The corresponding primary estimand is described by the following 5 attributes:

- Treatments: The randomized treatment administered BID until delivery (with at least 1 dose), regardless of adherence to randomized treatment, treatment modification, or treatment termination
- Population: Participants with ICP who have an sBA concentration  $\geq 20$   $\mu\text{mol/L}$  and an average daily score of  $\geq 4$  on the Adult ItchRO during the screening period. Further population criteria details are provided in [Sections 5.1](#) and [5.2](#).
- Endpoint: Change in the sBA concentration comparing baseline with Week 3
- Population-level summary: Difference in the mean change in the sBA concentration
- Intercurrent events:
  - Change in or administration of any allowed concomitant medication will be handled using a treatment policy strategy.
  - Administration of any prohibited concomitant medication will be handled using a hypothetical strategy assuming that the prohibited medications are not available and hence were not taken, so as to assess the treatment effect for the randomized treatment groups on top of allowed concomitant medication.
  - Discontinuation of randomized treatment due to all of the following reasons will be handled using a treatment policy strategy:
    - Lack of efficacy
    - Safety concerns
    - Lack of compliance to study treatment
  - Delivery prior to 3 weeks of treatment will be handled using a hypothetical strategy, assuming that delivery has not occurred. Few early deliveries are expected prior to Week 3. Participants with sBA  $< 100$  are not likely to give birth prior to 39 weeks, which is at least 3 weeks after the first dose date based on

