#### **10.4.2.4. Prior and Concomitant Treatments**

Prior and concomitant treatments will be summarized descriptively by treatment group with the number and proportion of participants.

Prior medications will be presented separate from concomitant treatments. Medications that started prior to the first dose of study medication will be considered prior medications regardless

of whether they were stopped prior to the first dose of study medication. Any medications continuing or starting after the first dose of study medication will be considered to be concomitant. If a medication starts prior to the first dose of study medication and continues after the first dose of study medication, it will be considered both prior and concomitant.

Medications will be coded using the World Health Organization Drug Dictionary.

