## **7.6. Changes From Protocol-Specified Safety Analyses**

There are no deviations from the protocol-specified safety analyses.

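### The SAP's concomitant medication summary stops at the last dose, so therapy started after stopping study drug is left out of it, contrary to the protocol's definition (minor)

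*SAP*

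**What the plan says.** SAP 4.3.2 contains two definitions. It opens with an unbounded one: "Concomitant medications are defined as medications taken after the first dose of study drug". The operational rule then adds an upper limit. A medication "started after the first dosing date but prior to or on the last dosing date of study drug will be considered concomitant medications", whereas one with "a start date after the last dosing date of study drug will be excluded from the concomitant medication summary".

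Protocol 10.4.2.4 has no upper limit: "Any medications continuing or starting after the first dose of study medication will be considered to be concomitant". Protocol 10.4.2 lists concomitant treatment usage among the safety measures. SAP 7.6 states: "There are no deviations from the protocol-specified safety analyses".

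Stopping study drug does not end follow-up. Protocol 7.1 asks that, where possible, "participants who discontinue study drug should continue in the study on a weekly visit schedule until completion of F2". Protocol Table 1 collects concomitant treatment at every visit through F2, and Protocol 6.8 requires medications received at any time in the study to be recorded.

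For the primary estimand, Protocol 10.4.1.1 states: "Change in or administration of any allowed concomitant medication will be handled using a treatment policy strategy". It applies the same strategy to discontinuation for lack of efficacy, safety concerns or noncompliance.

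**The concern.** The last dose and delivery coincide, or nearly so, for a woman who stays on study drug. For a woman who stops early they can be weeks apart, and in that interval she may start ursodeoxycholic acid (UDCA) or an antipruritic. Both are named as possible rescue medication in Protocol 6.8.1.2. The protocol calls such a drug concomitant; the SAP summary leaves it out.

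The by-arm medication table is where a reader looks to see what else participants were taking. Under the protocol's estimand, allowed therapy taken after stopping is part of what is compared at Week 3. Switching after stopping for lack of efficacy or poor tolerability could plausibly differ between volixibat and placebo. A table that omits those starts could make the arms look more alike in background therapy than they were.

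**Working it through.** No figure in the plan is at issue, so the check applies each rule to example dates.

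**Inputs.** The SAP rule is the inclusion and exclusion text of SAP 4.3.2. The protocol rule is 10.4.2.4. Days follow SAP 3.8.1, with the first dose on Day 1. The example has a last dose on Day 10 and delivery after Day 22. In SAP Table 2, Week 3 is nominal Day 3 × 7 + 1 = 22, with a window from 3 × 7 − 2 = 19 to 3 × 7 + 4 = 25.

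**Rules.** SAP summary: count if start day ≤ last dose day. Protocol: count if the drug continues or starts after the first dose.

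| Drug start | SAP summary | Protocol |
|---|---|---|
| Day 9 | counted | concomitant |
| Day 10 | counted | concomitant |
| Day 11 | not counted | concomitant |
| Day 15 | not counted | concomitant |

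A drug started on Day 11 or Day 15 precedes the Day 22 sample. If the woman stopped for one of the three treatment-policy reasons, the protocol's estimand keeps that sample. The drug is recorded at the weekly visits but does not enter the SAP table.

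**The listing.** The SAP's medication listing covers prior and concomitant medications. SAP 4.3.1 defines prior as taken before the first dose. Under the operational rule, a Day 11 start is neither prior nor concomitant, so a programmer could drop it. Under the section's opening sentence it is concomitant and would be listed. The SAP does not say which governs, while Protocol 10 expects all study data to be listed.

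**Limits of the rule.** Not every later start is lost. A partial start date in the same month as the last dose (or the same year, if the month is also missing) is not excluded, and a record with both dates missing is included. The exclusion applies when the start is known to fall after the last dose.

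**Size.** Per 100 women in an arm, let p stop before delivery, let a share f of these then start an ICP or antipruritic drug, and let d other women start one while on study drug. The share of users missed is p·f / (p·f + d). The documents give none of these values. Purely as assumptions:

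- p = 10, f = 0.5, d = 5: 5 / (5 + 5) = 50% missed.
- p = 20, f = 0.5, d = 5: 10 / (10 + 5) = 67% missed.
- f = 0: 0% missed, whatever p is.
- d = 0 with any start after stopping: 100% missed.

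If the first two cases were the two arms, true use of 10 versus 15 would be tabulated as 5 versus 5. The formula can give anything from 0% to 100%, so this shows the direction of the error and not its amount.

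**The case against.** The strongest reply is that this is one descriptive table with no planned testing, and that the therapy in question is examined elsewhere. SAP 6.3 compares by arm the proportion requiring rescue medication, and SAP 6.1.5 repeats the primary analysis without data collected after rescue begins. Neither has a stated cut-off at the last dose. That stands, and it limits the point to the summary and possibly the listing.

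A reader might infer that a woman who switches to UDCA after stopping is treated throughout the trial's results as having had no ICP therapy, or that the rescue endpoint is biased. The documents do not support either reading. The exclusion sentence is worded for the summary, her data are still recorded, and no section derives the rescue endpoint from this summary.

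The estimand argument also has limits. Protocol 6.8.2 prohibits ICP drugs other than permitted UDCA, and the protocol handles prohibited drugs hypothetically. Discontinuation for other reasons is hypothetical too. SAP 6.1.3 labels discontinuation as hypothetical generally, which is a separate conflict with the protocol. The reasoning about kept Week 3 data therefore rests on the protocol's estimand and on allowed therapy. Even so, identifying prohibited drugs after stopping requires a complete medication record under either approach.

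Protocol 6.8.1.2 also discourages rescue in the first 3 weeks, so early starts like those in the example may be uncommon. Their frequency is not given.

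Finally, the SAP states that it is based on protocol Version 1 of 14 October 2020. Whether SAP 7.6 was wrong against that version cannot be judged from these documents. Against the current protocol, the difference is present and undeclared.

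**Conclusion.** The mismatch is real and follows from the text alone. SAP 4.3.2 conflicts with Protocol 10.4.2.4 and with its own opening sentence. As written, it yields a by-arm table of a protocol-named safety measure that omits drugs known to have started after the last dose. The consequence is confined to women who stop before delivery. It is certain for the summary and possible for the listing. No primary, secondary or rescue result is shown to change, and the size of the undercount is unknown because stopping and switching rates are not given. Severity: minor.

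**What to change.** In SAP 4.3.2, remove the last-dose limit from both the inclusion and the exclusion sentence. Count medications started after the first dose and at least through delivery, whether or not study drug has been stopped. The protocol sets no end, so if the table closes at delivery, say so and record that as a change. Show starts after stopping study drug separately by arm, and make clear that the listing includes them. Add one sentence stating that identification of rescue and prohibited medication does not depend on the last-dose date.

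If an on-treatment table ending at the last dose is wanted, keep it, declare it as a change from the protocol, and add a companion table of starts after the last dose up to delivery.

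The cost is a few sentences in the SAP and one split or additional table. No new data collection is needed. The edit fits naturally into the SAP's update to the current protocol.

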#### **4.4. Protocol Deviations**

Participants who did not meet the eligibility criteria for study entry, but enrolled in the study will be summarized. The summary will present the number and percentage of participants who did not meet at least 1 eligibility criterion and the number of participants who did not meet specific criteria based on the ITT Analysis Set. A by-participant listing will be provided for those participants who did not meet at least 1 eligibility (inclusion or exclusion) criterion. The listing will present the eligibility criterion (or criteria if more than 1 deviation) that participants did not meet and related comments, if collected.

Protocol deviations occurring after participants entered the study are documented during routine monitoring. The number and percentage of participants with important protocol deviations by deviation reason (e.g., nonadherence to study drug, violation of select inclusion/exclusion criteria) will be summarized by indication for the ITT Analysis Set. A by-participant listing will be provided for those participants with important protocol deviations.

## **5. BASELINE CHARACTERISTICS**

### **5.1. Demographics**

Participants demographic variables (i.e., age, sex, race, and ethnicity) will be summarized using descriptive statistics for age, and using number and percentage of participants for sex, race, and ethnicity. The summary of demographic data will be provided for the ITT Analysis Set.

A by-participant demographic listing, including the informed consent date, will be provided by participant ID number in ascending order.

### **5.2. Other Baseline Characteristics**

Other baseline characteristics include height (cm), weight (kg), baseline PRO assessments (including 5-D Itch, CSS, EQ-5D-5L, PROMIS Fatigue & Sleep PROs, and PIS-Itch) and baseline levels of biochemical markers of cholestasis and liver disease (including total sBA, ALP, AST, ALT, bilirubin [total and direct], FGF-19, autotaxin, 7 $\alpha$ C4, progesterone sulfate, and GLP-1).

Additional disease-specific variables are discussed in [Section 5.4](#). These baseline characteristics will be summarized using descriptive statistics for continuous variables and using number and percentage of participants for categorical variables. The summary of baseline characteristics will be provided for the ITT Analysis Set. No formal statistical testing is planned.

A by-participant listing of other baseline characteristics will be provided by participant ID number in ascending order.

### **5.3. Medical History**

Medical history will be collected at screening for disease-specific and general conditions (i.e., conditions not specific to the disease being studied) and coded using Medical Dictionary for Regulatory Activities (MedDRA) version 23.1.

A summary of disease-specific medical history will be provided for the ITT Analysis Set.

Time since ICP diagnosis (weeks) will be calculated by (date of informed consent of study drug – date of ICP diagnosis)/7. Time since ICP diagnosis will be summarized using summary statistics for a continuous variable. The other variables will be presented using summary statistics for a categorical variable. No formal statistical testing is planned.

Menstrual history (e.g., last menstrual period [LMP] and date of positive human chorionic gonadotropin test), and obstetric history (e.g., previous pregnancies including terminations of pregnancy and/or spontaneous abortions, genetic screenings, aneuploidy screening, teratogen exposures since LMP/pregnancy, infections [i.e., Covid-19, Zika, HIV, or hepatitis], travel

outside the country, history of IVF or other fertility treatments, history of cerclage placement) will be obtained.

General medical history data will not be summarized, but will be listed.

A by-participant listing of disease-specific and general medical history will be provided by participant ID number in ascending order.

In deriving the time since ICP diagnosis, all partial dates of diagnosis will be identified, and the partial dates will be imputed as follows:

- If day and month are missing but year is available, then the imputed day and month will be 01 Jan.
- If day is missing but the month and year are available, then the imputed day will be the first day of the month.
- Partial date will not be imputed if the year is missing.

#### **5.4. Prior Antipruritic or Prior ICP Therapy**

The number of prior antipruritic and prior ICP therapies will be coded using the international reference for medicinal product information (WHODrug) 2020 March version or later and summarized by ATC drug class Level 2 and preferred name using the number and percentage of participants for each indication using descriptive statistics based on the ITT Analysis Set.

## **6. EFFICACY ANALYSES**

### **6.1. Primary Efficacy Endpoint**

#### **6.1.1. Definition of the Primary Efficacy Endpoint**

The primary efficacy endpoint analysis is defined as the mean change in total sBA concentration from baseline to Week 3.

#### **6.1.2. Estimand and Analysis of the Treatment Effect**

The estimand for the treatment effect will be the mean difference between volixibat and placebo for the change from baseline in sBA at Week 3.

The primary analysis will be conducted in the primary cohort using the modified ITT (mITT) population. A restricted maximum likelihood (REML)–based mixed-effects model for repeated measures (MMRM) will be used including weekly postbaseline change from baseline in total sBA during the core study period (double-blind treatment period) through Week 3, as the dependent variable and the fixed, continuous effects of baseline sBA and gestational age, fixed categorical effects of presence/absence of gestational diabetes, treatment group, visit, and treatment group by-visit interaction as covariates and participant as a random effect.

The unstructured variance/covariance matrix will be used to model the variances and covariances for the time points included in the model. The unstructured variance/covariance does not impose any restrictions on the pattern of the matrix elements. The use of an endpoint 3 weeks after baseline should result in minimal amounts of missing data. Every attempt (e.g., relaxing the convergence criteria, increasing the iteration limit, choosing reasonable starting values for the estimates) will be made to ensure convergence using the unstructured modeling of within-participant correlations. However, if the numerical algorithm for estimation of the mixed model fails to converge, the following variance/covariance matrix structures will be used in the following order: 1) heterogeneous Toeplitz, 2) heterogeneous compound symmetry, and 3) heterogeneous autoregressive of order 1. The first (co)variance structure that does not have a convergence problem will be the one used for the analysis. The Kenward-Roger approximation (1997) will be used to estimate denominator degrees of freedom.

The primary efficacy analysis will compare volixibat and placebo using the contrast (difference in least squares [LS] means) between treatment groups at Week 3. Significance tests will be based on LS means using a 2-sided significance level (2-sided 95% CIs).

The null hypothesis for the primary efficacy endpoint of the equality of volixibat and placebo is:

H0: mean change in total sBA baseline and Week 3 in the two treatment groups are equal

The null hypothesis of equal treatment effect will be rejected if the statistical analysis results in a 2-sided p-value for treatment at Week 3 is  $\leq 0.05$ . For each cohort, LS means will be calculated for each treatment group for each postbaseline visit in the model. The difference between volixibat and placebo change from baseline in sBA will be estimated, with the corresponding 2-sided 95% CI constructed for each visit through Week 3. The change from baseline LS means with standard error, 95% CI for the LS means, p-value for testing if the LS mean is zero, LS mean difference between treatment groups (volixibat minus placebo) with standard error, 95% CI for the LS mean difference, and p-value for testing if the treatment LS means are equal will be presented.

The study will be claimed successful if the hypothesis of no treatment effect on the primary efficacy endpoint over the primary cohort in the mITT population from Part 2 is rejected at the 0.05 (2-sided) significance level.

Summary statistics on total sBA by treatment group and visit will also be presented. In addition, a figure with the LS mean  $\pm$  standard error of change from baseline in total sBA will be presented by treatment group and visit.

In addition, a responder analysis (based on change in total sBA) may be considered.

Separately, a similar analysis on the open-label supplemental cohort will be performed. The analysis will be identical, except that baseline sBA will not be a covariate used within the model.

